8.4.1 Confidence interval precision of the difference in the expected mean VAS changes

Supposing to have a value of -20 mm for all the mean VAS changes (dryness, foreign body sensation, burning/stinging, itching, pain, stick feeling, blurred vision and photophobia) and a standard deviation σ of 10 mm (the 50% of the expected mean VAS change) in the Lubricin 20 µg/mL arm, Lubricin 50 µg/mL arm and Vismed® 0.18% arm, the number of subjects per treatment arm required in order to have a two-sided 95% confidence interval of the difference in means with a precision ω (defined as the length of the confidence interval divided by two) of 9 mm can be calculated according to the following formula (7):

$$N_{\text{per arm}} = \text{ceiling} \left(\frac{2 \sigma^2 z^2_{1-\frac{\alpha}{2}}}{\omega^2} \right)$$

α (2-sided)	ω (precision)	σ	$N_{\text{per arm}}$
0.05	9 mm	10 mm	10

8.4.2 Confidence interval precision of the difference in the expected proportions of subjects reporting at least one TEAE throughout the study

Supposing to have a proportion of subjects reporting at least one TEAE throughout the study of 0.15 (i.e. 15%) in the Lubricin 20 µg/mL arm (π_{T1}) and in the Lubricin 50 µg/mL arm (π_{T2}) and of 0.45 (i.e. 45%) in the Vismed® 0.18% arm (π_C), the number of subjects per treatment arm required in order to have a two-sided 95% confidence interval of the difference in proportions with a precision ω (defined as the length of the confidence interval divided by two) of 0.4 (i.e. 40%) can be calculated according to the following formula (8):

$$N_{per\ arm} = ceiling\left(\frac{z^2_{1-\frac{\alpha}{2}} [\pi_{T_j}(1-\pi_{T_j}) + \pi_C(1-\pi_C)]}{\omega^2}\right)$$

α (2-sided)	ω (precision)	π_{T_1}, π_{T_2}	π_C	$N_{per\ arm}$
0.05	40%	15%	45%	10

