3.2. Clinical Data

3.2.1 LUB0114MD: A MULTICENTER, RANDOMIZED, DOUBLE-MASKED, CONTROLLED, NON-INFERIORITY STUDY TO EVALUATE TOLERABILITY, SAFETY AND EFFICACY OF LUBRICIN EYE DROPS VERSUS SODIUM HYALURONATE EYE DROPS (OCUYAL®) ADMINISTERED FOUR TIMES A DAY FOR 4 WEEKS AND 1 WEEK FOLLOW-UP IN SUBJECTS WITH MODERATE DRY.

The study, which enrolled 56 subjects, was a multicentre, randomized (1:1), double-masked, controlled, non-inferiority study to evaluate the tolerability, safety and efficacy of Lubricin eye drops (monodose; 150µg/mL) versus with a widely used commercial 0.13% sodium hyaluronate eye drop formulation administered 4 times a day for 4 weeks in subjects with moderate dry eye disease.

The primary objective of this study was to demonstrate that lubricin 150 µg/mL is non-inferior to a widely used commercial 0.13% sodium hyaluronate eye drop formulation in improving signs and symptoms in patients with moderate dry eye.

Since the lubricin effect was expected to be similar to that of hyaluronic acid, it was hypothesised that the largest clinically acceptable effect to declare non-inferiority between treatments was a change in SANDE questionnaire results (Symptom Assessment iN Dry Eye) overall score (primary parameter) of 12 mm, with an estimated standard deviation (SD) of 13 (about 70% of mean at 28 days post-treatment).

Results obtained from this clinical investigation allow claiming the efficacy, the safety and the tolerability of use of the test IMD. The investigation results demonstrated the non inferiority of lubricin 150 µg/mL eye drops versus the comparator sodium hyaluronate 0.13% eye drops thus confirming the use intended for lubricin as ocular surface lubricant. No limitation in the use of lubricin 150 µg/mL eye drops, when used according to the recommendations provided, either as IMD in future clinical investigations or as marketed medical device, is envisaged as compared to sodium hyaluronate 0.13% eye drops. On the basis of the results and the observations done during the clinical investigation, the benefit/risk ratio observed for the test IMD did not differ from that of the comparator.

3.2.2 LUB0115MD: A 2 WEEK, RANDOMIZED, DOUBLE-MASKED, CONTROLLED, PARALLEL GROUP AND 1 WEEK FOLLOW-UP STUDY TO EVALUATE TOLERABILITY, SAFETY AND EFFICACY OF LUBRICIN (150 µG/ML) EYE DROPS VERSUS SODIUM HYALURONATE (HA) 0.18% EYE DROPS (VISMED®) IN PATIENTS WITH MODERATE DRY EYE (DE).

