6.1.5. Subjects Replacement

Discontinued subjects will not be replaced. Any patient who exits early from the study must undergo all procedures outlined in Visit 3.

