7.3 Expected Drop-out Rate

An anticipated 10% drop-out of the randomized subjects will be expected

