8.4 Sample size and power considerations

The expected mean VAS changes, the expected standard deviations and the expected proportions of subjects reporting at least one TEAE throughout the study used for the sample size calculation are not based on any clinical result or literature data since this information is not available for the comparison of the two concentrations of Lubricin (20 and 50 µg/mL) eye drops versus sodium hyaluronate (HA) 0.18% eye drops (Vismed®) in patients with ocular discomfort following refractive surgery.

Due to the exploratory nature of the investigation, the sample size calculation is based on the confidence interval precision of the difference in the expected mean VAS changes and of the difference in the expected proportions of subjects reporting at least one TEAE throughout the study; the confidence level α is set to 0.05 for all the confidence intervals without any formal adjustment for multiplicity.

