8.5 Handling of missing data

Not available data will be evaluated as "missing values". All data obtained will be used in the analysis and no imputation will be carried out for missing data to come from data not recorded in the CRF, from withdrawal of subjects from the study or from exclusion of subjects evaluated during the blind review meeting.

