8.11 Efficacy analysis

8.11.1 Primary efficacy analysis

The primary efficacy analysis will be performed on the subjects included into the Full Analysis Set.

Subjects will be analysed according to the treatment they actually received.

8.11.1.1 Tolerability using a Visual Analogue Scale (VAS) for dryness, foreign body sensation, burning/stinging, itching, pain, stick feeling, blurred vision and photophobia

The VAS values of each ocular symptom (i.e. dryness, foreign body sensation, burning/stinging, itching, pain, sticky feeling, blurred vision and photophobia) and their changes from day 1 - pre-dose values and day 15±2 - pre-dose values for the study/primary eye and for the non-study/secondary eye will be listed ([Listing 16.2.6.1](#)) and summarised by treatment and time point using descriptive statistics (mean, SD, CV%, minimum, median and maximum) ([Table 14.2.1.1](#)).

The VAS values of each ocular symptom for the study/primary eye and for the non-study/secondary eye will be analysed using an analysis of variance for repeated measures model. The model will include fixed effect terms for time point, baseline covariate (i.e. the day 1 - pre-dose value) and treatment. Time point will be specified as a repeated measurement. An unstructured covariance structure of the R matrix will be used and covariance parameters will be estimated using the restricted maximum likelihood method ([Table 14.2.2.1](#)).

Only the VAS values collected at Visit 1, Visit 2 and Visit 3 will be included into the analysis of variance for repeated measure model.

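### SAP 8.4.1's 9 mm VAS precision holds only if the SD is known to be 10 mm and nobody is lost; N = 10 per arm is correct, but the precision should be restated as approximate.

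*SAP*

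**What the plan says.** - SAP 8.4 states that "the sample size calculation is based on the confidence interval precision of the difference in the expected mean VAS changes", together with the precision of the difference in TEAE proportions. It adds that the planning values "are not based on any clinical result or literature data since this information is not available".
- SAP 8.4.1 supposes a mean change of -20 mm and an SD of 10 mm in every arm and for every symptom. It uses a normal-quantile formula and gives 10 per arm for a half-width "defined as the length of the confidence interval divided by two) of 9 mm can be calculated according to the following formula". No time point is named.
- Protocol 7.3: "An anticipated 10% drop-out of the randomized subjects will be expected". Protocol 6.1.5: "Discontinued subjects will not be replaced". Protocol 6.3.7 randomizes exactly 10 per arm.
- SAP 8.5: "All data obtained will be used in the analysis and no imputation will be carried out for missing data".
- SAP 8.11.1.1 analyses VAS with a repeated-measures model: "The model will include fixed effect terms for time point, baseline covariate (i.e. the day 1 - pre-dose value) and treatment". No treatment-by-time term is listed.
- Protocol 7.2 rests N on clinical feasibility, and SAP 8.3 calls the investigation exploratory.

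**The concern.** For VAS, interval precision is the SAP's only stated basis for 10 per arm. The 9 mm depends on two things the plan does not expect to have: an SD known in advance, and complete data on all 30 subjects. Someone planning a later study from 8.4.1 could take it that each VAS difference will be known to within 9 mm.

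A related gap lies in the model. With a single treatment effect and no treatment-by-time term, the on-treatment Day 15 difference is averaged with the other time points. These include Visit 3, by which time any topical treatment has been allowed (SAP 4.5.1). A difference at Day 15, where SAP 8.11.4 compares the secondary variables, is then not estimated separately.

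**Working it through.** **Inputs.** Two-sided 95% interval, half-width 9 mm, SD 10 mm (SAP 8.4 and 8.4.1); 10 per arm (protocol 6.3.7); 10% drop-out (protocol 7.3), which is 3 of 30, or one per arm if spread evenly.

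**1. The plan's own figure.** N = 2 × 10² × 1.96² / 9² = 9.485, rounded up to 10. Inverted, half-width = 1.96 × 10 × √(2/10) = 8.77 mm. The stated N reproduces.

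**2. Same formula with drop-out.**
- 9 per arm: 1.96 × 10 × √(2/9) = 9.24 mm.
- 9 against 10 (only one of the two compared arms loses a subject): 1.96 × 10 × √(1/9 + 1/10) = 9.01 mm.

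**3. SD estimated rather than known.** An unadjusted two-arm t interval with observed SD 10 mm has half-width t(0.975, 2n-2) × 10 × √(2/n).
- n = 10: 2.101 × 10 × 0.4472 = 9.40 mm.
- n = 9: 2.120 × 10 × 0.4714 = 9.99 mm.

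If the true SD is 10 mm, the chance that the realised half-width is 9 mm or less is 44% at 10 per arm and 33% at 9.

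**4. Sensitivity to the SD.** The half-width is proportional to the SD. By the SAP's formula, 10 per arm meets 9 mm only up to an SD of 9 / (1.96 × √0.2) = 10.27 mm. Losing one subject per arm multiplies the half-width by √(10/9) = 1.054, the same as an SD of 10.54 mm. So an SD error above about 5% outweighs the expected drop-out. The SDs of 8 and 15 mm below are assumptions:

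| SD (mm) | two-arm t, 10 per arm | two-arm t, 9 per arm |
|---|---|---|
| 8 | 7.52 | 7.99 |
| 10 | 9.40 | 9.99 |
| 15 | 14.09 | 14.99 |

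**5. Closer to the planned analysis.** As a stand-in for the repeated-measures model, take an ANCOVA of the Day 15 value on baseline and arm, with variance pooled over three arms. Assume normal data, equal variances at baseline and Day 15, and an SD of change of 10 mm. The residual SD is then 10 × √((1 + r)/2), where r is the baseline/Day 15 correlation. The t quantile has 3n - 4 degrees of freedom. Simulated mean half-width, allowing for chance baseline imbalance:

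| r (assumed) | 10 per arm | 9 per arm |
|---|---|---|
| 0.5 | 8.0 | 8.5 |
| 0.7 | 8.6 | 9.1 |
| 0.8 | 8.8 | 9.35 |
| 0.9 | 9.05 | 9.6 |

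At 10 per arm the mean stays within 9 mm up to a correlation of about 0.88. The documents give no correlation.

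**6. TEAE figure.** 1.96² × (0.15 × 0.85 + 0.45 × 0.55) / 0.4² = 9.003, rounded up to 10. At 9 per arm the half-width is 1.96 × √(0.375/9) = 40.0 points, so SAP 8.4.2 needs no change.

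**The case against.** The case for leaving 8.4.1 alone is substantial, and much of it stands.

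- **The SAP discloses the weakness.** The sentence saying the inputs have no clinical or literature source comes just before 8.4.1. That is fair, but the disclosure shows no consequence and only one SD is tried.
- **The plan's own inputs give 8.77 mm.** This is correct. The larger figures need a lost subject, an estimated SD, or both. A normal quantile is a common planning convention.
- **Nine per arm is pessimistic.** Early exits undergo the Visit 3 procedures, which include the VAS, and all observed data are used. The t figure exceeds 9 mm without any drop-out, however.
- **An unadjusted interval is not the planned analysis.** This is the strongest point. On the stand-in in step 5, the planned type of analysis stays within 9 mm at 10 per arm over most of the correlation range. The t figures are therefore a conservative reference, not a forecast.

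Three stronger readings are tempting, and the documents do not support them.

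- A reader might infer that the true half-width is about 12 mm, because protocol 3.2.1 plans the earlier lubricin study "with an estimated standard deviation (SD) of 13 (about 70% of mean at 28 days post-treatment". That figure belongs to the SANDE score in moderate dry eye. It may be the SD of a score rather than of a change: on that reading, with equal variances and a correlation of 0.7, the SD of change is 13 × √(2 × 0.3) = 10.07 mm, close to the SAP's value. It is not evidence about the VAS SD.
- A reader might infer that N is wrong or should be raised. N reproduces, rests on feasibility and serves an exploratory aim.
- A reader might infer that the SAP omits the difference intervals on which it bases N. SAP 8.1 sets rounding for confidence limits and the appendix is redacted, so an omission cannot be shown.

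**Conclusion.** The point holds as a minor one. N = 10 per arm is arithmetically correct, but the 9 mm half-width is conditional on a known SD of 10 mm and no loss of subjects. Against 8.77 mm on the plan's own inputs, the figure is 9.01 to 9.24 mm with the expected drop-out, and 9.40 to 9.99 mm for an unadjusted two-arm t interval with an observed SD of 10 mm. Baseline adjustment may bring it back to 9 mm or below, depending on a correlation nobody has stated. The SD is the larger uncertainty, as the SAP in effect admits.

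This rests on drop-out of one per arm with no usable Day 15 data (the pessimistic end), on Day 15 as the time point of interest (8.4.1 names none; 8.11.4 compares changes there), and on the single-time-point ANCOVA as a stand-in for the repeated-measures model.

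**What to change.** Keep 10 per arm and leave 8.4.2 unchanged.

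Restate 8.4.1 along these lines:

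> The number per arm rests on feasibility. With an observed SD of change of 10 mm, the half-width of an unadjusted two-arm, two-sided 95% t interval is about 9.4 mm at 10 per arm and about 10.0 mm if 9 per arm have Day 15 data; this is a conservative reference. For a baseline-adjusted three-arm analysis, the expected half-width is about 8.0 to 9.05 mm at 10 per arm and 8.5 to 9.6 mm at 9 per arm, for assumed baseline/Day 15 correlations of 0.5 to 0.9. All figures scale with the SD: over an assumed range of 8 to 15 mm, the two-arm t half-width at 10 per arm is 7.5 to 14.1 mm.

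Do not cite the SANDE SD of 13 as support for the VAS SD.

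In 8.11.1.1, add a treatment-by-time term. From that model, report each Lubricin-minus-Vismed difference at Day 15 pre-dose in the study/primary eye with its 95% CI, labelled descriptive and unadjusted for multiplicity. The on-treatment difference is then not averaged with Visit 3.

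The cost is SAP wording, one model term and one table of 16 intervals (8 symptoms × 2 comparisons), with no more patients, visits or data. The downside is a slightly less favourable stated precision and a few extra parameters in a 30-subject fit.

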8.5 Handling of missing data

Not available data will be evaluated as "missing values". All data obtained will be used in the analysis and no imputation will be carried out for missing data to come from data not recorded in the CRF, from withdrawal of subjects from the study or from exclusion of subjects evaluated during the blind review meeting.

8.6 Study/Primary eye identification

If just one eye is treated, that is the "Study/Primary eye". If both eyes are treated, the worst one (highest VAS average score) is chosen as "Study/Primary eye"; in the event average VAS score is equal in both eyes, right eye is chosen as "Study/Primary eye". The other eye is referred to as "Non-study/Secondary eye".

8.7 Demographic, baseline and background characteristics

Demographic, baseline and background characteristics will be reported for all the subjects included into the Enrolled Set.

Subjects will be analysed according to the treatment they actually received.

8.7.1 Subjects' disposition

The disposition of all subjects enrolled in the study will be listed ([Listing 16.2.4.1](#)) and summarised by treatment ([Table 14.1.1.1](#)). The number and proportion of subjects enrolled, randomized, treated and completing the study, the number and proportion of withdrawals and the reasons for withdrawal will be presented.

8.7.2 Analysis sets

The subjects included in each analysis sets will be listed ([Listing 16.2.4.2](#)) and summarised by treatment ([Table 14.1.1.2](#)).

8.7.3 Subjects excluded from efficacy and /or safety analysis

All subjects excluded from the efficacy and /or safety analysis will be listed and the reasons for exclusion will be reported ([Listing 16.2.3.1](#)).

8.7.4 Discontinued subjects

All subjects who discontinued the clinical investigation (if any) will be listed. Last device administered before discontinuation, gender, age, last visit performed before discontinuation,

time elapsed from last device administration (days), date of premature discontinuation and primary reason for subject premature discontinuation will be reported ([Listing 16.2.1.1](#)).

8.7.5 Protocol deviations

All the protocol deviations reported during the clinical investigation will be listed ([Listing 16.2.2.1](#)) and summarised by treatment. The number and proportion of subjects for each deviation will be reported ([Table 14.1.1.5](#)).

8.7.6 Blind breaking

The date and the reason of any blind breaking will be listed ([Listing 16.2.2.2](#)).

8.7.7 Demography

Demographic data will be listed ([Listing 16.2.4.3](#)) and summarised by treatment ([Table 14.1.1.3](#)). The number and proportion of subjects in each category for categorical variables (e.g. race) and descriptive statistics (mean, SD, CV%, minimum, median and maximum) for continuous variables (e.g. age, weight) will be presented.

8.7.8 Inclusion/exclusion criteria not met

All the unmet inclusion/exclusion criteria will be listed ([Listing 16.2.4.4](#)) and summarised by treatment ([Table 14.1.1.4](#)).

8.7.9 Medical, ocular and surgical history

All the diseases of medical and ocular medical history and the surgeries of all subjects enrolled in the study will be coded using the Medical Dictionary for Regulatory Activities (MedDRA) version 20.1, listed ([Listing 16.2.10.1](#)) and summarised by treatment ([Table 14.1.1.6](#)). The number and proportion of subjects with any findings will be presented by PT and SOC.

8.7.10 Prior and concomitant medication

All prior and concomitant medications will be coded using the World Health Organization Drug Dictionary Enhanced (WHODDE) September 2017 and listed by treatment ([Listing 16.2.10.2](#)).

Prior medications will be summarized by treatment ([Table 14.1.1.7](#)). The number and proportion of subjects with any concomitant medication will be presented by and ATC 4th level (or the higher available ATC level if 4th level is missing) and standardised drug name.

Concomitant medications will be summarized by treatment ([Table 14.1.1.8](#)). The number and proportion of subjects with any concomitant medication will be presented by and ATC 4th level (or the higher available ATC level if 4th level is missing) and standardised drug name.

8.7.11 Subjects' study visits

The dates of all subjects study visits will be listed by treatment ([Listing 16.2.10.3](#)).

8.8 Investigational device administration at site

The date and time of device administration at site for the study/primary eye and for the non-study/secondary eye will listed by treatment and time point ([Listing 16.2.5.1](#)).

8.9 Investigational device accountability

The identifier of the dispensed kit, the dispensation date and visit, the number of dispensed multidose vials, the return date and visit and the number of returned multidose vials will listed by treatment ([Listing 16.2.5.2](#)).

8.10 Lubricin concentrations

The date and time of tears collection, the Lubricin concentrations for right eye and left eye and their changes from pre-dose values for right eye and left eye at day 1 and day 15±2 will be listed by treatment ([Listing 16.2.5.3](#)). BLQL values will be imputed as zeros for calculating the changes from pre-dose.

8.11 Efficacy analysis

8.11.1 Primary efficacy analysis

The primary efficacy analysis will be performed on the subjects included into the Full Analysis Set.

Subjects will be analysed according to the treatment they actually received.

8.11.1.1 Tolerability using a Visual Analogue Scale (VAS) for dryness, foreign body sensation, burning/stinging, itching, pain, stick feeling, blurred vision and photophobia

The VAS values of each ocular symptom (i.e. dryness, foreign body sensation, burning/stinging, itching, pain, sticky feeling, blurred vision and photophobia) and their changes from day 1 - pre-dose values and day 15±2 - pre-dose values for the study/primary eye and for the non-study/secondary eye will be listed ([Listing 16.2.6.1](#)) and summarised by treatment and time point using descriptive statistics (mean, SD, CV%, minimum, median and maximum) ([Table 14.2.1.1](#)).

The VAS values of each ocular symptom for the study/primary eye and for the non-study/secondary eye will be analysed using an analysis of variance for repeated measures model. The model will include fixed effect terms for time point, baseline covariate (i.e. the day 1 - pre-dose value) and treatment. Time point will be specified as a repeated measurement. An unstructured covariance structure of the R matrix will be used and covariance parameters will be estimated using the restricted maximum likelihood method ([Table 14.2.2.1](#)).

Only the VAS values collected at Visit 1, Visit 2 and Visit 3 will be included into the analysis of variance for repeated measure model.

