 - e. not willing to use highly effective birth control measures, such as: Hormonal contraceptives – oral, implanted, transdermal, or injected and/or mechanical barrier methods – spermicide in conjunction with a barrier such as a condom or diaphragm or IUD during the entire course of and 30 days after the study treatment periods.

TEST Investigational Medical Device, Dosage and Mode of Administration:*Treatment period:*

Sterile isotonic aqueous solution for ocular administration containing Lubricin 20 $\mu\text{g}/\text{ml}$ eye drops solution or Lubricin 50 $\mu\text{g}/\text{ml}$. In all patients, both eyes will be treated, unless only one eye meets the eligibility criteria. If just one eye is treated, that will be the "Study/Primary eye". If both eyes are

treated, the worst one (highest VAS average score) should be chosen as "Study/Primary eye"; in the event average VAS score was equal in both eyes, right eye will be chosen as "Study/Primary eye". The investigator will administer the morning study dose on Day 1 then patients will self-administer the drops at home/site, as applicable.

Eligible patients will self-administer 1 drop of Lubricin 20 µg/ml or Lubricin 50µg/ml in the eye(s) which underwent refractive surgery three times a day (TID) approximately every 6h for 2 weeks.

No other ocular topical treatments allowed, including artificial tears/lubricants.

Follow-up period:

Follow-up period of 7 days, any ocular topical treatments allowed, including other artificial tears/lubricants as prescribed by the treating physician.

Duration of Investigational Device Treatment:

Treatment duration 14 days (2 weeks) ±2 days (maximum treatment duration 16 days).

Follow-up period of 7 days, any ocular topical treatments allowed, including other artificial tears/lubricants as prescribed by the treating physician.

REFERENCE Investigational Medical Device, Dosage and Mode of Administration

Treatment period:

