Visit 1 – Day 1 - Dose

- At the completion of the pre-dose assessments, the investigator will administer the study product (morning dose) into the eligible eye(s)

Visit 1 – Day 1 – 15 minutes post-dose

- Assessment of ocular tolerability (Visual analogue scale, VAS: dryness, foreign body sensation, burning/stinging, itching, pain, stick feeling, blurred vision and photophobia)
- Tear collection for Lubricin dosing in the right eye

Visit 1 – Day 1 – 30 minutes post-dose

- Assessment of ocular tolerability (Visual analogue scale, VAS: dryness, foreign body sensation, burning/stinging, itching, pain, stick feeling, blurred vision and photophobia)
- Tear collection for Lubricin dosing in the left eye
- The Investigator will deliver to the patients the investigational medical device for the treatment period (15±2 days)

At home: From Day 1 to Week 2 Visit:

- Self-administration at home of the Investigational medical device TID approximately every 6h into the eligible eye(s)

Visit 2 – Week 2 ± 2 Days (prior the morning dose)

- Review of current medical conditions (ocular and systemic: including External Ocular Examination)
- AE and concomitant medications
- Ocular examination in both eyes, consisting of the assessments detailed for the baseline visit (points 1-10), in the same order and with the same intervals
- Urine Pregnancy test (only female)

Visit 2 – Week 2 ± 2 Days - Dose

- At the completion of the pre-dose assessments, the investigator will administer the study product (morning dose) into the eligible eye(s)

Visit 2 – Week 2 ± 2 Days – 15 minutes post-dose

- Assessment of ocular tolerability (Visual analogue scale, VAS: dryness, foreign body sensation, burning/stinging, itching, pain, stick feeling, blurred vision and photophobia)
- Tear collection for Lubricin dosing in the right eye

Visit 2 – Week 2 ± 2 Days – 30 minutes post-dose

- Assessment of ocular tolerability (Visual analogue scale, VAS: dryness, foreign body sensation, burning/stinging, itching, pain, stick feeling, blurred vision and photophobia)
- Tear collection for Lubricin dosing in the left eye

Visit 3 – Final Follow-up Visit - 7±2 days after last administration (day 22 ± 2)

- Review of current medical conditions (ocular and systemic: including External Ocular Examination)

- AE and concomitant medications
- Ocular examination in both eyes, consisting of the assessments detailed for the baseline visit (points 1-10), in the same order and with the same intervals

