6.1.4. Methods and Equipments for Endpoints Recordings

6.1.4.1. Ocular evaluations

Ocular evaluations will be performed on both eyes. The assessments must always be performed according the sequence (1 – 10) detailed in § 6.1.3. The assessment will be performed at visit 1 (day 1), 2 (day 15±2), 3 (day 22±2))/early termination visit.

The ophthalmological assessment will include:

1. **Visual analogue scale (VAS):** Local ocular tolerability score: A global ocular discomfort score will be determined using a 100 mm VAS
2. **Symptom Assessment in Dry Eye (SANDE):** Subjects with SANDE overall score ≥ 30 mm are eligible for enrolment\randomization. The SANDE questionnaire is a short questionnaire to evaluate both dry eye intensity and frequency by using a 100 mm VAS.
3. **Best corrected distance visual acuity (BCDVA):** Subjects with best corrected distance visual acuity (BCDVA) score of ≥ 0.1 decimal units in both eyes are eligible for enrolment\randomization. Refraction and visual acuity measurements will be performed for all subjects by trained vision examiners only.

Equipment: Refraction equipment required includes:

- Retroilluminated Light box and ETDRS 4 meter distance acuity chart set
- Trial lens frames
- Trial lens set with plus or minus cylinder lenses
- Jackson cross-cylinders of 0.25, 0.50, and 1.00 diopters
- Pinhole occluder
- Tissues or eye pads and tape
- A 1 meter rigid measuring stick

4. **Slit lamp examination (SLE):** The slit lamp examination must be performed before the instillation of any dilating or anesthetic eye drops or the fluorescein agent.

The subject will be seated at the slit lamp while being examined. Grading of the eyelids, 1 lashes, conjunctiva, cornea, lens, iris and anterior chamber will be done.

5. **Central corneal sensitivity by Cochet-Bonnet aesthesiometry:** The Cochet-Bonnet aesthesiometer contains a thin, retractable, nylon monofilament that extends up to 6 cm in length. Variable pressure can be applied to the cornea by adjusting the monofilament length. The monofilament length ranges from 6 to 0.5 cm. As the monofilament length is decreased the pressure increases from 11 mm/gm to 200 mm/gm.

Corneal sensation will be measured in the affected eye(s) in the central area of the cornea using a Cochet Bonnet aesthesiometer before the instillation of any dilating or anesthetic eye drops.

Start the procedure by testing the corneal sensitivity within the area (center) of the PED or corneal ulcer of the affected eye.

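### SAP 8.6 and 8.11 let undosed fellow eyes be analysed under a device arm, so non-study-eye results can mix exposed and unexposed eyes

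*SAP*

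**What the plan says.** **Dosing.** The protocol synopsis (1.1) says: "In all patients, both eyes will be treated, unless only one eye meets the eligibility criteria". At the site visits, "the investigator will administer the study product (morning dose) into the eligible eye(s". For home dosing, the synopsis directs the drop elsewhere: "in the eye(s) which underwent refractive surgery three times a day (TID".

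**Assessment.** Protocol 6.1.4.1: "Ocular evaluations will be performed on both eyes". An undosed eye therefore yields data at every visit.

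**Labelling.** SAP 8.6 makes the treated eye the study eye when only one is treated, and the worse eye the study eye when both are. It closes with "The other eye is referred to as" the non-study/secondary eye, and sets no condition that this eye was dosed.

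**Analysis.** SAP 8.11.1.1 says the VAS scores "for the study/primary eye and for the non-study/secondary eye will be analysed using an analysis of variance for repeated measures model". On the terms: "The model will include fixed effect terms for time point, baseline covariate (i.e. the day 1 - pre-dose value) and treatment". No term marks whether the eye received the device. The per-eye secondary endpoints (8.11.4.1 to 8.11.4.4 and 8.11.4.6 to 8.11.4.8) are summarised by treatment for both eyes. Their between-treatment tests do not say which eye is used. The arm label is the treatment the subject received, not what the eye received.

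**Safeguards.** SAP 8.11.2 and 8.11.3 plan no sensitivity or subgroup analysis, and 6.3 has no stratification. Site dosing per eye is listed (8.8) but not used in any analysis.

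**The concern.** An eye that never received a drop cannot show whether the drop is tolerated or works. If such eyes are counted as Lubricin or Vismed eyes, two things can happen to the fellow-eye output. Its mean change and any arm difference are diluted. With 10 subjects per arm and no stratification, arms may also differ by chance in the number of one-eye subjects, and that shows up as a difference between devices. VAS tolerability is a primary endpoint and is modelled for both eyes, so readers will look for agreement between the two sets of results.

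**Working it through.** **The plan's own figure.** SAP 8.4.1: N = 2σ²z²/ω² = 2 × 10² × 1.96² / 9² = 9.49, rounded up to 10 per arm. This reproduces. With 10 per arm the half-width is 1.96 × 10 × √(2/10) = 8.77 mm.

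**Inputs.** From SAP 8.4.1: mean change −20 mm and SD 10 mm, taken to describe dosed eyes. Assumed, because the documents give neither: the share u of fellow eyes that are undosed, and their mean change m0.

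**Mean and spread of the pooled fellow eye.** Mean = (1−u)(−20) + u·m0. SD = √(10² + u(1−u)(20+m0)²).

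| u | mean, m0 = 0 | SD, m0 = 0 | mean, m0 = −10 | mean, m0 = −20 |
|---|---|---|---|---|
| 10% | −18 | 11.7 | −19 | −20 |
| 20% | −16 | 12.8 | −18 | −20 |
| 30% | −14 | 13.6 | −17 | −20 |

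The dilution of the mean change halves at m0 = −10 mm and vanishes at −20 mm.

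**A true 10 mm difference between devices.** Take −30 v −20 mm in dosed eyes, with the same u in both arms. The expected difference in unadjusted change is (1−u) × 10 = 9, 8 or 7 mm at u = 10%, 20% or 30%. The figures were run with m0 = 0, but m0 cancels if undosed eyes change alike in both arms.

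**Chance imbalance, identical devices.** Three more undosed eyes in one arm of 10 shift the unadjusted difference by 0.3 × (20+m0). That is 6 mm at m0 = 0 (for example 1 v 4 undosed: 0.9 × −20 = −18 v 0.6 × −20 = −12), 3 mm at m0 = −10 and 0 at m0 = −20. With independent binomial counts, the chance that two arms of 10 differ by three or more undosed eyes is 6%, 16% and 22% at u = 10%, 20% and 30%.

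**Type I error.** In 100,000 simulated trials per u (m0 = 0, t test on change, 10 v 10, as a stand-in for the planned model), the mean arm difference was about 0 and the nominal 5% test rejected in 4.9% to 5.0%. Among trials with an imbalance of three or more, it rejected in about 15%.

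**Effect of the baseline covariate, at one time point.** Assume baseline VAS of 45 mm in dosed eyes and 15 mm in undosed eyes, with changes of −20 and 0. Later values are then 25 and 15 mm. With 1 v 4 undosed of 10:
- Later means: 0.9 × 25 + 0.1 × 15 = 24 v 0.6 × 25 + 0.4 × 15 = 21, a gap of 3 mm.
- Baseline means: 0.9 × 45 + 0.1 × 15 = 42 v 0.6 × 45 + 0.4 × 15 = 33, a gap of 9 mm.
- Adjusted gap: 3 − 9b for pooled baseline slope b. This is 0 at b = 1/3 and 2.4 mm in size at b = 0.6.

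If undosed eyes start as symptomatic as dosed eyes, adjustment removes nothing and the gap stays at 6 mm.

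**Precision with dosed fellow eyes only.** Half-width 1.96 × 10 × √(2/n): 9.24, 9.80 and 10.48 mm for n = 9, 8 and 7 per arm. Pooled half-widths at u = 10%, 20% and 30% are 10.22, 11.22 and 11.89 mm if m0 = 0, and 9.15, 9.44 and 9.64 mm if m0 = −10. Restriction improves precision in the first case and costs a little in the second.

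**The case against.** **The definition may be narrower.** In SAP 8.6 the sentence naming the other eye follows the rule for two treated eyes, so it could mean only a second treated eye. SAP 8.8 fits that reading, since it lists device administration for the non-study eye with no proviso. This reading is possible, but nothing in 8.6 or 8.11 enforces it. A programmer following the text would include the undosed eye.

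**One-eye subjects may be few.** The visual acuity criterion applies to both eyes, and several exclusions (acuity, infection, other surface disorders, recent dry-eye medication, other surgery) apply to either eye and so remove the subject. What remains is mainly an unoperated eye or one with average VAS below 25 mm. This stands: if no one-eye subject is enrolled, there is no effect.

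**No change in undosed eyes is an extreme assumption.** Protocol section 3 describes symptoms after surgery as usually short-lived, so some improvement without drops is plausible. On the other hand, an eye scoring below 25 mm has little room to fall by 20 mm. The range above covers both.

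**A stronger reading is tempting.** A reader might infer that any arm imbalance in one-eye subjects passes straight into the VAS treatment effect, or that the comparison is biased. Neither is supported. The VAS model adjusts for baseline, which can absorb much of the gap when undosed eyes start low. Eye eligibility is settled before randomisation, so imbalance arises only by chance.

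**The trial is exploratory.** SAP 8.3 rests no regulatory claim on it and disclaims formal testing against control. That lowers the stakes, but does not make a mixed estimate interpretable.

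**Conclusion.** The point holds as a minor one. As worded, the SAP puts undosed fellow eyes under a device label whenever one-eye subjects are enrolled. At 10% to 30% undosed, a 10 mm difference in unadjusted change is seen as 9 to 7 mm. A three-eye chance imbalance moves unadjusted arm means by up to 6 mm, against the SAP's 9 mm precision target, and by less in the baseline-adjusted model if undosed eyes have low starting scores. These sizes rest on assumed values for the undosed share and, for the imbalance shift, on no change in undosed eyes.

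It should not be read as a threat to the trial's main results. The study eye is always dosed, adverse events are counted by subject, the sample size of 10 per arm does not depend on the fellow eye, and overall type I error is not inflated.

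A separate inconsistency remains: site dosing refers to eligible eyes and home dosing to operated eyes. The two can differ, for instance for an operated eye with average VAS below 25 mm. Until they are reconciled, it is not settled which fellow eyes count as dosed.

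**What to change.** In SAP 8.6 and 8.11, state that non-study-eye summaries, models and any tests include only fellow eyes that received the device. List undosed fellow eyes separately, and report the number of one-eye and two-eye subjects per arm. Reconcile the protocol passages on which eyes receive drops; this review takes no position on which should stand.

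The cost is SAP wording, one dosed-eye flag derivable from the site-administration listing (16.2.5.1), and a table row. The downside is a smaller n in fellow-eye tables, and the loss need not be equal across arms: with 1 v 4 undosed of 10, the comparison has 9 v 6 eyes. Because eye eligibility is assessed before randomisation, the restriction does not break the randomised comparison. It should be made before database lock and unblinding.
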